# Eligibility

# Inclusion Criteria

In order to be eligible to participate in this study, the patients must meet all of the following criteria:

- At least 18 years of age
- Confirmed COVID-19 disease (by Cobas SARS-CoV-2 real time reverse transcription polymerase chain reaction (RT-PCR) using nasopharyngeal swab sample, or equivalent test available to be performed by the Columbia University Irving Medical Center (CUIMC)/New York Presbyterian (NYP) clinical laboratory). Effort will be made to have the confirmatory test result <72 hours prior to enrollment however given overall clinical demand this may not be feasible in all cases.
- Respiratory failure manifesting as: Acute Respiratory Distress Syndrome (defined by a P/F ratio of <200), OR oxygen saturation (SpO2) < 90% on 4 liters (L) (actual or expected given higher O2 requirement) OR increasing O2 requirements over 24 hours, plus 2 or more of the following predictors for severe disease:

- CRP > 35 mg/L Ferritin > 500 ng/mL D-dimer > 1 mcg/L Neutrophil-Lymphocyte Ratio > 4 Lactate dehydrogenase (LDH) > 200 U/L Increase in troponin in patient w/out known cardiac disease
- Has a consent designee willing to provide informed consent on behalf of the patient (this
  assumes that a mechanically ventilated patients lacks capacity to consent on his/her own behalf.
  Should it be deemed that the patient has capacity to consent, consent may be obtained from
  the patient.)
- Women of childbearing potential must be willing and able to use at least one highly effective contraceptive method for a period of 5 months following the study drug administration. In the context of this study, an effective method is defined as those which result in low failure rate (i.e. less than 1% per year) when used consistently and correctly such as:
  - combined (estrogen and progestogen containing) hormonal contraception combined (estrogen and progestogen containing) hormonal contraception (oral, intravaginal, or transdermal)
  - progestogen-only hormonal contraception associated with inhibition of ovulation (oral, injectable, implantable)
  - intrauterine device (IUD)
  - intrauterine hormone-releasing system (IUS)
  - vasectomized partner
  - o bilateral tubal occlusion
  - true abstinence. when this is in line with the preferred and usual lifestyle of the subject.
     Periodic abstinence, such as calendar, ovulation, symptothermal, postovulation methods, and withdrawal are not acceptable methods of contraception.
- Men must be willing to use a double-barrier contraception from enrollment until at 5 months after the last dose of study drug, if not abstinent.

# Exclusion Criteria

An individual who meets any of the following criteria will be excluded from participation in this study:

- Evidence of irreversible injury deemed non-survivable even if the pulmonary failure recovers (for example severe anoxic brain injury)
- Known active inflammatory bowel disease
- Known active, untreated diverticulitis
- Known untreated bacteremia

- Pregnancy. (The protocol will exclude pregnant subjects given the lack of overall data on use of clazakizumab in pregnancy however the study team would consider a protocol revision should more than 3 potential pregnant study subjects be excluded on this basis).
- Known hypersensitivity to the clazakizumab

## **Strategies for Recruitment and Retention**

The patients enrolled will be identified by the members of the Columbia University Irving Medical Center / New York Presbyterian Hospital (CUIMC/NYPH) COVID-19 inpatient team who have identified the potential subject as critically ill and failing all available medical and supportive therapies. Patient recruitment will begin by direct communication between the COVID-19 inpatient team and the study team. An individual involved in the patient's care must determine and document that the patient or their surrogate (if the patient lacks capacity) has agreed to discuss the study with the researchers. Duration of Study Participation

The entire duration of study participation is 60 days. Study specific laboratory tests will be performed within the first 14 days of study initiation. Beyond 14 days, all data collected will be that which is acquired for purposes of clinical care. Patients will be followed for the survival endpoint for 60 days. Total Number of Participants and Sites

The CUIMC/NYP inpatient hospital site is expected to enroll up to30 patients across the 2 arms. NYU will serve as the central data managing site, and will analyze data from patients enrolled at NYU, Columbia, and Johns Hopkins. Total enrollment is expected to be 150 patients across three sites. Expected contribution of patients will be: NYU Langone (New York, NY): 90 total patients (80 already randomized 1:1:1 and 10 to be randomized 1:1 for high-dose clazakizumab 25mg vs placebo) Johns Hopkins Medicine (Baltimore, MD): 30 patients to be randomized 1:1 for high-dose clazakizumab 25mg vs placebo New York-Presbyterian/Columbia University (New York, NY): 30 patients to be randomized 1:1 for high dose clazakizumab 25mg vs placebo Columbia and Johns Hopkins will contribute de-identified data to the central dataset but the conduct of the trial at each site will be overseen by the local IRB the respective sites.

## Participant Withdrawal or Termination

The predicted mortality rate for patients with COVID-19 and ARDS is in excess of 50% (7). As such we anticipate there will be mortality amongst some of the participants. Death will constitute withdrawal from the trial. Otherwise we would not anticipate premature withdrawal from the study as the patients are expected to remain hospitalized (likely in an ICU setting) for the entire duration of the 14-day period where study specific data are collected. If the patient is discharged before day 28 survival status will be obtained by patient lookup in the electronic medical record. For discharged patients in whom there is no definitive record documenting patient status (alive or dead) after 28 days have elapsed, the study team will contact the patient or patient's family by phone to assess patient survival and to assess for the occurrence of any interim AEs/SAEs. At end of study (day 60), a phone call will also take place to assess patient survival and again asses for interim AEs/SAEs. The IP administration will occur over a maximum of 3 days following enrollment. Study specific laboratory tests will be performed in the first two weeks and if a patient (or consent designee should the patient lack capacity) wishes to withdraw from participation and refuse these laboratory studies, they will be free to do so.

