## **Study Design and Endpoints**

This is a randomized, double-blind, placebo-controlled, design. We propose the administration of an investigational drug in patients with high predicted short-term mortality secondary to COVID-19 disease. 30 Patients will be randomly assigned in a 1:1 ratio to two study arms that will receive clazakizumab at a dose of 25 mg or placebo.

Primary Study Endpoints

The primary endpoint is patient safety assessed by serious adverse events associated with clazakizumab or placebo.

Secondary Study Endpoints

The secondary endpoints are: incidence of intubation, time to extubation, length of ICU stay, trend in C-reactive protein, severity of AKI, need for RRT, duration of RRT, and patient survival at 28 and 60 days.

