(This visit pertains only to subjects who remain inpatient at this time. If discharged, we will collect available data from the medical record.)

Day 14 laboratory studies

Collection of clinical data (vital signs, laboratory results, hemodynamic parameters, respiratory parameters, RRT)

Day 28 +/- 3:

Phone visit for documentation of survival status and assessment of interval AE/SAEs Collection of clinical data (laboratory results indicating kidney function, RRT)

Day 60 +/- 5:

Phone visit for documentation of survival status and assessment of interval AE/SAEs Collection of clinical data (laboratory results indicating kidney function, RRT)

Additional clinical data to be collected:

- Date of symptom onset
- Date of intubation (if performed)
- Date of extubation (if performed)
- Date of tracheostomy (if performed)
- Dates of initiation/discontinuation and type of renal replacement (if performed)

- Use and duration of prone positioning (if performed)
- Date of ICU discharge (if occurs)
- Date of hospital discharge (if occurs)
- Date of death (if occurs)

Additional data to be collected if testing becomes available during the conduct of this trial: Assessment of SARS-CoV-2 viral load by quantitative RT-PCR in blood. This would be tested at enrollment and on day7 if this assay becomes available and able to be performed in the New York Presbyterian Hospital CUIMC Clinical Laboratory.

Should the patient choose to withdraw from the study before the 60 day study duration has elapsed, the patient's choice to withdraw will be documented. The patient will be followed by the medical record to collect clinical data obtained for standard clinical care as pertains to the study outcomes.

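### The protocol gives two rules for the Day-28 contact; under one, enquiry about serious adverse events depends on whether the chart shows survival status

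*Combined protocol and SAP*

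**What the plan says.** Study Design and Endpoints makes SAEs the primary outcome: "The primary endpoint is patient safety assessed by serious adverse events".

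Two places then describe the contact at Day 28.

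- **Participant Withdrawal or Termination** starts with a chart lookup: "If the patient is discharged before day 28 survival status will be obtained by patient lookup in the electronic medical record". A call follows, once 28 days have passed, for a subset introduced by "For discharged patients in whom there is no definitive record documenting patient status (alive or dead". For these patients the team is to "contact the patient or patient's family by phone to assess patient survival and to assess for the occurrence of any interim AEs/SAEs". The same section adds a Day-60 call on survival and AEs/SAEs and attaches no condition about the record.
- **The detailed Schedule of Events**, under Study Procedures, has this entry at Day 28 ± 3: "Phone visit for documentation of survival status and assessment of interval AE/SAEs". The Day 60 ± 5 entry is worded the same way. Neither is restricted to a subset.

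The paragraph on recording adverse events, just before the Statistical and Analytical Plans, tells the investigator to ask about AEs and SAEs at every study visit.

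**The concern.** The withdrawal section joins two tasks that need different triggers. Whether a patient is alive at Day 28 can often be settled from the chart. Whether the patient has had an SAE since discharge often cannot. An entry showing survival does not show that no event was treated at another hospital. Yet under that section the entry removes the call, and the AE/SAE questions go with it. The schedule would have the same patient called.

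Two coordinators following different sections would therefore collect the primary endpoint differently. Under the withdrawal section, whether SAEs are asked about at Day 28 depends on an unrelated fact: whether a definitive chart entry exists. At stake are the completeness and uniformity of SAE ascertainment after discharge.

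**Working it through.** No figure in the plan depends on the Day-28 rule, so there is none to reproduce. The check compares the texts and then works out the recall intervals.

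1. **Trigger.** Withdrawal section: discharge before Day 28 leads to a record lookup, and a call is made if nothing definitive is found. Schedule: a phone visit at Day 28 ± 3, with no condition.
2. **Is the schedule's silence meaningful?** It limits visits where it intends to. Days 7 and 14 carry the note "This visit pertains only to subjects who remain inpatient at this time". Day 28 has no such note, so its natural reading is that it applies to everyone.
3. **Both rules applied to two discharged patients.** Patient A has a chart entry showing survival; patient B has none. Under the schedule both are called and asked about SAEs. Under the withdrawal section only B is.
4. **What else covers patient A?** Once a patient is discharged, the Day-7 and Day-14 entries fall back on available chart data. For someone discharged before Day 14, Day 28 is thus the first scheduled direct enquiry after discharge. If it is skipped, the next is Day 60 ± 5.
5. **Length of recall.** For discharge on day d and a call on day c, recall since discharge is c − d.
   - d = 14: 28 − 14 = 14 days at Day 28; 60 − 14 = 46 days at Day 60.
   - d = 27: 28 − 27 = 1 day; 60 − 27 = 33 days.
   - d = 6 with both calls at the end of their windows: 31 − 6 = 25 days; 65 − 6 = 59 days. This is an extreme case, since the protocol expects patients to stay in hospital through the 14-day period.
   - Delay in enquiry: 60 − 28 = 32 days nominally. Across the windows it runs from 55 − 31 = 24 to 65 − 25 = 40 days.
6. **Number affected at this site.** 30 × (share discharged before Day 28) × (share of those with a definitive record). The documents give neither share, so the product cannot be evaluated.
7. **Scale of one missed case.** With 15 patients per arm, one patient whose only SAE goes unrecorded lowers that arm's SAE rate by 1/15 = 6.7 percentage points. The plan's maximum 95% CI width of 0.52 for 15 patients (exact calculation 0.521) reflects sampling error only and would not reveal such a loss.

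**The case against.** The strongest reply is that the schedule is the operative text. It plans the visit for everyone, and AE/SAE enquiry is required at each visit. The withdrawal section mainly explains how survival is traced after discharge. It never says in terms that calls are made only when the record is silent, so it can be read as a backstop. Part of this stands: the harm arises only if staff follow the withdrawal section. But that section attaches the AE/SAE questions to the conditional call, so it does describe how SAEs are collected, and nothing says which section prevails.

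The second reply is the Day-60 call. It carries no such condition and will recover many events in survivors. That stands and bounds the harm.

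Several stronger readings are tempting but not supported.

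- **All sites affected.** A reader might apply the rule to the 120 patients in the two main arms (60 each). This document randomises 30. Conduct at each site is under its local IRB, and nothing shows that this wording governs the other two sites.
- **A guessed count.** A reader might assume discharge and coverage shares. A high share such as 60% discharged alive by Day 28 would conflict with the expected mortality of about 50%.
- **Patients who die between the calls are never covered.** The protocol names the family as an informant for the conditional Day-28 call, and dates of death are collected. These patients could not be interviewed themselves, so SAEs could be missed; that is as far as the text goes.
- **Follow-up calls are barred after Day 14.** The sentence "Beyond 14 days, all data collected will be that which is acquired for purposes of clinical care" directly follows one on study-specific laboratory tests and most naturally contrasts routine data with those tests. The protocol plainly plans later calls, so the sentence is weak support.
- **Bias between arms.** The rule does not refer to arm and the trial is double-blind. Bias would need discharge or record availability to differ by arm, which is not shown.

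**Conclusion.** The two sections contradict each other on the Day-28 contact and should be reconciled, because the difference bears on how the primary endpoint is collected. If the withdrawal section is followed, discharged patients with a definitive record get no Day-28 AE/SAE enquiry. For survivors who are reached at Day 60, the cost is later enquiry with longer recall. For those who die or are lost between Days 28 and 60, SAEs could be missed. Patients still in hospital at Day 28 are not touched by the lookup rule.

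The number affected is unknown and no bias between arms or sites is established. The conclusion assumes only that the sections are read as worded and that a chart entry on survival is not a complete source of SAEs. It is a correction worth making, not a threat to the trial's validity.

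**What to change.** Reconcile Participant Withdrawal or Termination to the schedule. State that every patient discharged alive receives the AE/SAE enquiry at Day 28 and Day 60 whether or not the record documents survival, and that the family is asked if the patient cannot be interviewed or has died. Keep the record lookup for vital status and as a supplementary source of events, so that it no longer decides who is asked.

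The cost is a one-sentence change. The calls are already in the schedule, and no sample size or analysis changes.

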# Randomization

All enrolled subjects will be assigned a unique subject number, and the Investigator will maintain a list of subject numbers and subject names. A total of 30 subjects will be randomized (via an IRT) 1:1 into the 2 treatment arms using a stratified block randomization scheme: 15 subjects in the clazakizumab 25mg group and 15 subjects in the placebo group. In order to randomize the subject, the study coordinator or investigator will enter the unique subject number and data into a centralized database system. Subjects

meeting all clinical, site, and core lab inclusion/exclusion criteria will then be randomized to either the clazakizumab 25mg or placebo groups and will be registered as randomized. The randomization schema will be pre-prepared by a blinded statistician and will be made available only to the investigational pharmacy. All study investigators and clinical staff administering study drug will be blinded to the content of the dose. Detailed information on enrollment and randomization will be provided in the manual of operations.

## Blinding

This study is double-blind and therefore neither the Investigator, the subject, the Sponsor and its representatives, nor other designated study site personnel involved in running of the study will be aware of the identification of the investigational drug administered to each subject. To maintain blinding, interim analyses will be conducted by the designated independent study monitor. Detailed procedures for maintaining the blind are specified below. Given that clazakizumab and placebo are packaged differently, investigational drug will be prepared and dispensed by an unblinded pharmacist/qualified personnel at each investigational site. To maintain blinding during the study, the pharmacist/designated staff will dispense either clazakizumab or placebo into identical infusion bags, according to each subject's randomized treatment allocation, and all subjects will receive each dose of investigational drug (clazakizumab or placebo) as an intravenous infusion. The pharmacist/designated staff will not have access to drug supply records. In the event of suspected unexpected serious adverse event(s), the blinding may be broken in the best interest of and to provide the appropriate care for the affected participant.

## **Study Procedures**

This is a randomized, double-blind, placebo-controlled, adaptive seamless Phase II/III design (ASD). The investigators propose the administration of an investigational drug in patients with high predicted short-term mortality secondary to COVID-19 disease. Patients will be enrolled and randomly assigned in a 1:1 ratio to two study arms that will receive clazakizumab at a dose of 25 mg or placebo. Experimental: Clazakizumab Group

The first dose will be administered as soon as possible after the patient is enrolled and randomized into the Clazakizumab 25 mg arm. The route of administration will be intravenous. Each dose will be administered as an infusion that is run over 30 minutes. Serum C-reactive protein (CRP) will be evaluated at baseline and on days 1 and 2 following clazakizumab administration. If the CRP does not decrease by 50% within 36-48 hours after the first dose, a second dose of 25 mg clazakizumab will be given no later than day 3.

# Placebo Comparator: Placebo Group

The first dose will be administered as soon as possible after the patient is enrolled and randomized into the Placebo arm. The route of administration will be intravenous. Each dose will be administered as an infusion that is run over 30 minutes. Serum CRP will be evaluated at baseline and on days 1 and 2 following clazakizumab administration. If the CRP does not decrease by 50% within 36-48 hours after the first dose, a second dose of placebo will be given no later than day 3.

A detailed Schedule of Events Screening (Days -5 to 1): Inclusion and exclusion criteria verified Informed consent signed Medical history and physical exam documented (physical examination as conducted by subject's clinical care team) Concomitant medications documented Calculation of baseline H-score (see attached documents) for scoring sheet

Baseline study labs drawn (CRP must be drawn on same day as infusion of Investigational Product; prior to infusion of Investigational Product)

Collection of clinical data (vital signs, respiratory and hemodynamic support parameters) Day 1:

Day 1 laboratory studies (CRP, if screening and Day 1 are not performed on the same day) Physical examination (as conducted by subject's clinical care team)

Infusion of clazakizumab 25mg or placebo

IV Collection of clinical data (vital signs, respiratory and hemodynamic support parameters) Day 2 No window:

Day 2 laboratory studies Physical examination (as conducted by subject's clinical care team) Collection of clinical data (vital signs, respiratory and hemodynamic support parameters) Day 3 No window:

Day 3 laboratory studies Physical examination (as conducted by subject's clinical care team) Assessment of eligibility for repeated clazakizumab dose

Infusion of clazakizumab 25mg or placebo IV if criteria met

Collection of clinical data (vital signs, respiratory and hemodynamic support parameters, RRT) Day 4 No window:

, Day 4 laboratory studies

Day 5 No window:

Day 5 laboratory studies

Day 6 No window:

Day 6 laboratory studies

Day 7 + 1:

(This visit pertains only to subjects who remain inpatient at this time. If discharged, we will collect available data from the medical record)

Day 7 laboratory studies

Collection of clinical data (vital signs, laboratory results, hemodynamic parameters, respiratory parameters, RRT)

Day 14 +/- 2:

(This visit pertains only to subjects who remain inpatient at this time. If discharged, we will collect available data from the medical record.)

Day 14 laboratory studies

Collection of clinical data (vital signs, laboratory results, hemodynamic parameters, respiratory parameters, RRT)

Day 28 +/- 3:

Phone visit for documentation of survival status and assessment of interval AE/SAEs Collection of clinical data (laboratory results indicating kidney function, RRT)

Day 60 +/- 5:

Phone visit for documentation of survival status and assessment of interval AE/SAEs Collection of clinical data (laboratory results indicating kidney function, RRT)

Additional clinical data to be collected:

- Date of symptom onset
- Date of intubation (if performed)
- Date of extubation (if performed)
- Date of tracheostomy (if performed)
- Dates of initiation/discontinuation and type of renal replacement (if performed)

- Use and duration of prone positioning (if performed)
- Date of ICU discharge (if occurs)
- Date of hospital discharge (if occurs)
- Date of death (if occurs)

Additional data to be collected if testing becomes available during the conduct of this trial: Assessment of SARS-CoV-2 viral load by quantitative RT-PCR in blood. This would be tested at enrollment and on day7 if this assay becomes available and able to be performed in the New York Presbyterian Hospital CUIMC Clinical Laboratory.

Should the patient choose to withdraw from the study before the 60 day study duration has elapsed, the patient's choice to withdraw will be documented. The patient will be followed by the medical record to collect clinical data obtained for standard clinical care as pertains to the study outcomes.

The PI will record all reportable events related to the Infusion of the Investigational Product with start dates occurring any time after informed consent is obtained until 7 (for non-serious AEs and SAEs) after the last day of study participation. At each study visit, the investigator will inquire about the occurrence of AE/SAEs since the last visit. Events will be followed for outcome information until resolution or stabilization. All unresolved adverse events should be followed by the investigator until the events are resolved, the subject is lost to follow-up, or the adverse event is otherwise explained. At the last scheduled visit, the investigator should instruct each subject to report any subsequent event(s) that the subject, or the subject's personal physician, believes might reasonably be related to participation in this study. The investigator should notify Vitaeris of any death or adverse event occurring at any time after a subject has discontinued or terminated study participation that may reasonably be related to this study. Vitaeris should also be notified if the investigator should become aware of the development of cancer or of a congenital anomaly in a subsequently conceived offspring of a subject that has participated in this study.

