## Statistical and Analytical Plans (SAP)

Descriptive statistics for the safety endpoints will be used. With 10 patients, the 95% confidence interval (CI) around the rate of SAEs will be no more than 0.62 units wide. With 20 patients (combining the low dose and high-dose groups), the 95% CI will be no more than 0.46 units wide. Regarding the secondary outcome of patient survival, too little is known about the expected clinical behavior of these patients to make meaningful projections about expected changes in mortality given drug efficacy. Data will be analyzed across three sites: NYU, where this protocol originated; Columbia/NYP; and Johns Hopkins.

The first 80 patients at NYU were enrolled in the three-arm study using a 1:1:1 ratio. Following the DSMB's recommendation, additional NYU patients (expected to be 10) will be randomized in a 1:1 ratio to placebo or 25 mg clazakizumab. Columbia/NYP and Johns Hopkins will each enroll 30 patients in a 1:1 randomization ratio, with 15 patients each on clazakizumab 25mg and placebo. At these other sites, with 15 patients, the 95% confidence interval (CI) around the rate of SAEs will be no more than 0.52 units wide. The total planned enrollment of 150 subjects across these three sites will considerably increase the power to detect treatment effects. The table below summarizes approximate power for the projected sample size in the placebo and 25 mg clazakizumab groups (N=60 in each arm) to detect various reductions in mortality from the expected 50% rate in the placebo group, for various levels of Type I error (alpha) assuming use of a two-sided test. For example, we have approximately 82% power

to detect a reduction in the mortality rate of 50%, from 0.5 in the placebo group to 0.25 in the treated group, assuming 60 patients per group, at the usual Type I error rate of 0.05.

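### Baseline severity and pre-infusion CRP are scheduled at baseline, but the SAP prespecifies no covariate, and no test, for survival or CRP trend

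*Combined protocol and SAP*

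**What the plan says.** **Baseline data.** The schedule of events (under Placebo Comparator: Placebo Group) lists "Calculation of baseline H-score" at screening, a CRP sample on the infusion day before dosing, and "Collection of clinical data (vital signs, respiratory and hemodynamic support parameters".

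**Population.** Inclusion Criteria opens with "Respiratory failure manifesting as: Acute Respiratory Distress Syndrome (defined by a P/F ratio of <200" and then offers two alternatives: low saturation on 4 L of oxygen, or a rising oxygen need over 24 hours. The consent criterion anticipates ventilated patients. Study Design and Endpoints lists incidence of intubation as an outcome, so some patients are expected to enter unventilated.

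**Analysis.** The SAP section states descriptive statistics for safety, confidence-interval widths for the SAE rate, and approximate power to "detect various reductions in mortality from the expected 50% rate in the placebo group". The worked example goes "from 0.5 in the placebo group to 0.25 in the treated group", with "N=60 in each arm", "assuming use of a two-sided test" and "at the usual Type I error rate of 0.05". Survival at days 28 and 60 and the CRP trend are secondary endpoints. No test, model or covariate is named for either.

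**Randomisation.** The Randomization section specifies stratified blocks, does not name the strata, and leaves detail to the manual of operations.

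**The concern.** The entry criteria mix patients on rising oxygen with patients already ventilated, so the risk of death at entry is likely to vary a good deal. When outcome depends strongly on something known before dosing, adjusting for it gives a more powerful comparison from the same patients. The same holds for CRP, where the baseline value usually predicts the later one.

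The choice has to be made in advance. An adjusted model chosen after unblinding carries little weight, because the covariates could have been picked for the answer they give. With about 60 patients per arm, a visible chance difference in severity between arms would also leave the mortality result open to argument, with no planned analysis to settle it.

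**Working it through.** **1. Reproduce the plan's power.** Inputs from the SAP section: p0 = 0.50, p1 = 0.25, n = 60 per arm, two-sided alpha 0.05. For the unadjusted two-proportion z-test with pooled variance:

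- Pooled rate = (0.50 + 0.25)/2 = 0.375
- Null SE = sqrt(2 × 0.375 × 0.625/60) = 0.0884
- Alternative SE = sqrt((0.50 × 0.50 + 0.25 × 0.75)/60) = 0.0854
- Power = Φ((0.25 − 1.96 × 0.0884)/0.0854) = Φ(0.90) = 0.816

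This matches the stated 82%. Other unadjusted forms give 0.818 (arcsine), 0.833 (unpooled) and 0.759 (continuity-corrected). The arm size also fits the enrolment plan: 80/3 + 5 + 15 + 15 = 61.7.

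**2. Mortality power with one baseline score.** The documents give no prognostic strength, so it was varied. In 4,000 simulated trials per scenario, with 60 per arm, one normal baseline score and marginal risks held at 0.50 and 0.25, the adjusted test is the logistic likelihood-ratio test for treatment.

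| AUC of score (assumed) | Unadjusted power | Adjusted power | Adjusted type I error |
|---|---|---|---|
| 0.50 | 0.8133 | 0.8180 | 0.0520 |
| 0.64 | 0.8148 | 0.8345 | 0.0483 |
| 0.69 | 0.8233 | 0.8573 | 0.0493 |
| 0.74 | 0.8180 | 0.8855 | 0.0565 |
| 0.81 | 0.8253 | 0.9273 | 0.0580 |

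The gain runs from essentially nothing (AUC 0.50) to 0.9273 − 0.8253 = 0.102, about 10 points.

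**3. Several covariates.** With ventilation yes/no, age and site/stage in the model, one simulation raised power from about 0.81 to 0.83, 0.84, 0.86 and 0.91 at AUC 0.62, 0.65, 0.69 and 0.80. Another gave gains of about 0 to 7 points over an unadjusted 0.82 to 0.84, with likelihood-ratio type I error of roughly 0.05 to 0.07. The benefit is somewhat smaller than with a single score, and the slight excess in type I error is a reason to report a robust or bootstrap interval. None of these powers was computed for the standardised risk difference itself.

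**4. CRP.** No SD or correlation is given. Set the effect so that a comparison of post-dose values alone has 80% power: delta = (1.96 + 0.842) × sqrt(2/60) = 0.51 SD. With baseline correlation ρ, ANCOVA multiplies the SD by sqrt(1 − ρ²), and a change score multiplies it by sqrt(2(1 − ρ)).

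| ρ (assumed) | Post-dose only | Change score | ANCOVA |
|---|---|---|---|
| 0 | 0.80 | 0.51 | 0.80 |
| 0.3 | 0.80 | 0.66 | 0.84 |
| 0.5 | 0.80 | 0.80 | 0.90 |
| 0.7 | 0.80 | 0.95 | 0.98 |

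At ρ = 0.3, a change score gives up 0.84 − 0.66 = 0.18 against ANCOVA, so leaving the CRP method open has a price.

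**5. Chance imbalance.** If half the patients are ventilated at baseline and severity is not a stratum, two independent Binomial(60, 0.5) counts differ by 6 or more (10 points) with probability 0.315, about 32%.

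**6. Number of covariates.** Expected deaths are 60 × 0.50 + 60 × 0.25 = 45. That supports two or three prognostic covariates and no long list.

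**The case against.** The strongest reply is that the plan commits to no unadjusted analysis. Sizing a trial with a two-proportion formula is routine and does not fix the final test. A reader might infer that the plan discards power by design; the documents do not support that, because they name no method for either endpoint. This stands: any loss depends on what is eventually done, and the more basic gap is the missing efficacy method.

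Four further limits also stand.

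- A reader might infer that baseline CRP is used nowhere. It is the reference for the second-dose rule, and a trend would naturally start from it. It is only not specified as a covariate.
- The stratified blocks may already balance severity. With the strata unnamed, this can be neither confirmed nor ruled out, and the 32% figure would fall if severity were a stratum.
- A reader might apply the imbalance argument to one site with 15 per arm. No efficacy comparison of that size is planned: the SAP analyses data across three sites and uses 15 per arm only for an SAE interval width.
- Chance imbalance does not bias the randomised test or inflate its type I error. It costs precision and credibility.

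The documents also do not link the H-score to mortality; the Rationale section mentions only ferritin and IL-6, without effect sizes. P/F ratio is one of several entry routes and may not exist for every patient. None of this removes the case for fixing the adjusted analysis in advance.

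**Conclusion.** The point holds as a low-cost improvement to the secondary analyses. Baseline respiratory support, H-score and pre-infusion CRP are scheduled, none is specified as a covariate, and the only mortality calculation is an unadjusted one.

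The likely gain is about 0 to 10 points of mortality power for one continuous score, and somewhat less with several covariates. For CRP it is 4 to 18 points over a comparison of post-dose values alone, at correlations of 0.3 to 0.7. All of these figures rest on assumed prognostic strength or correlation, on 60 per arm and, for mortality, on rates of 0.50 and 0.25. The gain is nil if the covariates do not predict outcome.

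The validity of the randomised comparison is not in question, and the descriptive safety primary endpoint is unaffected.

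**What to change.** Add to the SAP, before unblinding:

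- **Mortality at days 28 and 60 (25 mg versus placebo):** logistic regression adjusted for baseline ventilation (yes/no), age, site/stage and any randomisation strata. Report a standardised risk difference with a robust or bootstrap confidence interval, and keep the unadjusted comparison as support. Ventilation status is a safer covariate than P/F ratio, which may be missing for some patients.
- **CRP:** ANCOVA of log CRP at named post-dose days on log same-day baseline CRP.
- **Randomisation:** name the strata and use them in these analyses.

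The cost is SAP wording and a few lines of code, with no new patients or measurements. The small downside is that the two or three prognostic covariates must be fixed in advance. NYU's second stage is expected to have only 10 patients, so the SAP should also say how such a small site/stage level is handled.
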